-		/caregivers will be recruited for the ECHO		
Deemvitus ant Deviced	Intervention effectiveness study.			
Recruitment Period	12 months			
Follow Up Period		post-intervention follow-up		
Overall Study Duration	16 months	·		
		Assess ECHO Intervention effectiveness evidenced		
Research Question/Aim(s)	through improved communication skills of children at 12-			
	week follov			
		effectiveness of a targeted intervention (ECHO) munication skills of children under 24 months		
		cant language difficulties and social		
Study Objectives		ation difficulties. To evaluate if there is any		
	noticeable	pticeable effect of the targeted intervention on the parent-		
	child intera	ction and parent/caregiver wellbeing.		
Primary Outcome Measure	н .	Primary Endpoint		
The Communication and Symbolic	Behaviour			
Scales Developmental Profile™ (C		Score at 12-week follow-up		
Secondary Outcome Measures		Secondary Endpoints		
Qualitative interviews		Qualitative Study results collected at interview,		
		at baseline and at 12-week follow-up		
WellComm Language Screen Early		,		
Toolkit – paper version (GL Assessments,		Score at 12-week follow-up		
2015)				

Manchester Local Care Organisation MANCHESTER CITY COUNCIL	Departr for Educ		Manchester Universit	S S
The Pragmatics Profile of Everyday Communication Skills (Dewart et a	,			
The Tool to Measure Parenting Se (TOPSE) (Bloomfield et al., 2010)	lf-Efficacy			
Clinical outcome measure of paren interaction	ıt-child	Score at ea up	ch session and at 12-week follow-	

Funding and Support in Kind

Funder(s)	Financial And Non-Financial Support Given Detail financial and non-financial support given by each organisation listed	
Department of Education	Funding for ECHO Intervention Development and Delivery, and Study of ECHO Intervention Effectiveness	
Manchester Local Authority	Funding for ECHO Intervention Development, and Study of ECHO Intervention Effectiveness	

Role of Study Sponsor and Funder

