Referrals received from health visiting service and/or children centre services. Eligibility and recruitment at initial visit.

Inclusion criteria: Parent/caregiver of child aged under 24 months at the start of intervention; Child Scored Red on WellComm Language Screen within 3 months of the referral; Child Scored High Likelihood of autism on Social Attention and Communication Surveillance (SACS-R) tool; Residing within the Manchester Local Authority for the duration of intervention.

Exclusion criteria: The family are currently receiving intervention from another Speech and Language Therapy Service; Parent/caregiver already taking part in the trial with another child; The child or parent has a diagnosis of visual, motor, or hearing impairment; The child has a diagnosis of a developmental disorder other than autism; Current significant and ongoing safeguarding concerns.

n = 40

Measures taken at baseline visit

Primary Outcome measure: The Communication and Symbolic Behaviour Scales Developmental Profile™ (CSBS DP)

Secondary Outcome measures:

The WellComm Language Screen; The Pragmatics Profile of Everyday Communication Skills; Clinical Outcome Measure Form (child's interaction, non-verbal communication skills, and language skills); The Tool to Measure Parenting Self-Efficacy (TOPSE); A research tool developed from local clinical service recording observations of parent-child interaction

5 ECHO intervention sessions delivered weekly

(Clinical outcome measure of parent-child interaction collected each session)

DEPENDED AND	
SR (#	
	100000
•	
10000	100
	100
10000	100
	-
	-
	-
10000	-
	-
	-
	-
	-
	-
	-
	-
	-
	-
	-
	-
	-
	-
	-
	-
	-
	-
	-
	-
	-
	-
	-

Measures taken 12 weeks following intervention

Primary Outcome measure: The Communication and Symbolic Behaviour Scales Developmental Profile™ (CSBS_DP)

Secondary Outcome measures:

The WellComm Language Screen; The Pragmatics Profile of Everyday Communication Skills; Clinical Outcome Measure Form (child's interaction, non-verbal communication skills, and language skills); The Tool to Measure Parenting Self-Efficacy (TOPSE); A research tool developed from local clinical service recording observations of parent-child interaction

1. Background

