3.2 Outcome Measures

Qualitative Study Outcomes:

i. In-depth semi-structured interviews with parents/caregivers who received the ECHO Intervention as part of their usual pathway of care.

ECHO Intervention Study Outcomes:

- i. Primary Outcome Measure: The Communication and Symbolic Behaviour Scales Developmental Profile™ (CSBS_DP) (Wetherby, A.; Prizant, B., 2002)
- ii. Secondary Outcome Measures, measured at baseline and 12-week follow-up (Parent-Child Interaction Pre/Post also taken at each intervention session)
- The Tool to Measure Parenting Self-Efficacy (TOPSE) (Bloomfield et al., 2010)
- Parent-Child Interaction Pre/Post Measure, a clinical tool used in current clinical practice to measure parent-child interaction strategy use
- WellComm Language Screen Toolkit Early Years Paper version (GL Assessments, 2015)
- The Pragmatics Profile of Everyday Communication Skills (Dewart, H., & Summers, S., 1995) to measure changes in child's communication skills

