4.3 Schedule of Procedures

Qualitative Study

Procedures	ECHO Intervention sessions 1-5 (Received as part of standard clinical practice*)	Review (Standard clinical practice 12 weeks after session 5)	Telephone call (At least 24 hours after review)	Interview (Within 12 months of session 5)**
Recruitment for Qualitative Study		X		
Telephone call to discuss participation queries			X	-
Interview			· ·	X

* Participants for the Qualitative Study do not need to participate in the ECHO Intervention Study

** Interviews will be conducted a minimum of 24 hours after Review session

ECHO Intervention Study

Department for Education

· · · · · · · · · · · · · · · · · · ·	ECHO Intervention Study visits (7)			
Procedures	Screening	Baseline (Minimum 24 hrs after screening)	ECHO Intervention sessions 1-5***	Review ^{****} (12 weeks after session 5)
Recruitment for ECHO Intervention Study	X		••••••••••••••••••••••••••••••••••••••	
Informed consent		Х		· ·
Demographics	· · · · ·	Х	· · · · · · · · · · · · · · · · · · ·	
All ECHO Intervention Study outcome measures collected		×		X
Parent-Child Interaction Pre/Post Measure completed		X	X	x

***May be conducted between 3 and 21 days after previous visit (including baseline visit)

****May be conducted up to 4 weeks before or after the 12-week window

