5.1.1 Inclusion Criteria

Qualitative Study:

- Parent/caregiver received at least one ECHO Intervention session within the last 12 months.
- Parent/caregiver residing within the Manchester Local Authority at the time of interview.
- Parent/caregiver having a sufficient level of oral language skills in any language to participate in an in-depth interview as assessed by the researcher's judgement.

ECHO Intervention Study:

- Parent/caregiver of a child aged less than 24 months at the start of intervention.
- Parent/caregiver of a child who scored Red on the WellComm Language Screen within 3 months of the start of intervention.
- Parent/caregiver of child who scored High Likelihood of autism on Social Attention and Communication Surveillance (SACS-R) tool.
- Residing within the Manchester Local Authority for the duration of intervention.

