The quantitative secondary measures, the TOPSE, and parent-child interaction clinical measures will be presented as an overall score, with appropriate descriptive statistics at baseline and the endpoint. The TOPSE will be scored according to validated methods described in the TOPSE Manual (Bloomfield et al., 2010) and the parent-child interaction clinical measure will be scored according to current clinical practice. Differences between the two timepoints will be examined using paired t-tests or Wilcoxon signed-rank tests. Exploratory analyses will also examine these measures at an item level to identify any responses where the difference in scores between baseline and review is distinctive compared to other items in that measure. Boxplots will be used to illustrate the spread of the differences for each item.

WellComm Screen results will be presented as the number and percentage (with 95% binomial confidence intervals) of children who score Red, Amber, and Green at review. All children will score Red at baseline as this is part of the eligibility criteria. Children scoring Amber or Green at review indicates that they have made clinically significant progress as Red indicates significant language difficulties, Amber indicates mild to moderate language difficulties, and Green indicates no language difficulties.

The Pragmatics Profile provides qualitative data consisting of parents' descriptions of their child's communication which will be analysed using the descriptive method as recommended by the Pragmatics Profile manual (Pragmatics Profile of Everyday Communication Skills).

Confounding variables such as maturation effects cannot be controlled for in this study and any significant effects identified will need to be further studied in a randomised control trial to

Date: 16.05.2024

control for confounding variables. This analysis is therefore to be considered as hypothesis generating.

2. Ethical and Regulatory Considerations

7.1 Risks and Burdens to Participants and Researchers (if applicable depending on the study intervention)

Families participating in the study will receive the same intervention and number of visits as families not participating in the study as the study aims to assess the effectiveness of standard clinical care. Participants should not be at any increased risk compared to families accessing standard clinical care outside of the study.

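### Section 6.1 labels any child who is not Red on one review WellComm as clinically progressed, but Red is also the entry cut-off, so the label is not supported by the rule

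*Protocol*

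**What the plan says.** Entry to the ECHO Intervention Study requires a Red WellComm. Section 5.1.1 has "Parent/caregiver of a child who scored Red on the WellComm Language Screen within 3 months of the start of intervention"; the flow chart ties the same criterion to a different date, "Child Scored Red on WellComm Language Screen within 3 months of the referral". Under either wording the qualifying screen can precede the baseline visit by weeks or months.

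WellComm is also a study outcome. Section 3.2 lists it under "Secondary Outcome Measures, measured at baseline and 12-week follow-up", and the section 4.3 schedule has all outcome measures taken at the baseline visit and at one review. That review has a tolerance: "May be conducted up to 4 weeks before or after the 12-week window". The Study Summary gives the endpoint as "Score at 12-week follow-up".

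Section 6.1 sets the analysis: "WellComm Screen results will be presented as the number and percentage (with 95% binomial confidence intervals) of children who score Red, Amber, and Green at" (the time point named is the review visit). It does not use the baseline measurement: "All children will score Red at baseline as this is part of the eligibility criteria". It then interprets the result: "Children scoring Amber or Green at review indicates that they have made clinically significant progress as Red indicates significant language difficulties". Section 5.3.2 confirms that there is no comparison group. Section 6.1 closes by naming maturation as an uncontrolled confounder and calling the analysis hypothesis generating.

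**The concern.** The line a child must be below to enter is the line the child must be above to count as progressed. When children are selected on a low reading and measured again, some of those near the line cross it even if nothing about them has changed. This is regression to the mean, and it occurs whenever retest reliability is below 1. The rule has no safeguard against it: no minimum score change, no repeat screen, no reference rate, and no use of the category measured at baseline.

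Increasing the child's language skills is a stated secondary objective (section 3.1), and WellComm is the only outcome to which section 6.1 attaches a label of clinical significance child by child. The results go to the Department of Education and the Local Authority (section 9.1). A percentage carrying that label would be read as language progress, although part of it may come from the rule.

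**Working it through.** **The plan's own figures.** The protocol gives no expected WellComm rate, so there is none to reproduce. The only number taken from the plan is the expected number of completers: 40 recruited, 10% dropout (section 5.3.1), 40 × 0.9 = 36.

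**Assumptions, none of them in the documents.**
- r, retest reliability of the score behind the colour bands: 0.80, 0.90, 0.95.
- q, share of screened children who are Red: 15%, 30%, 50%.
- SACS-R selection: severity correlated 0.5 or 0.7 with the stable language trait, with the most severe 30% of Red children retained as High Likelihood.
- No treatment effect, no maturation, normal scores, independent noise at each screen.
- Central case: q = 30%, r = 0.90.

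**Step 1: selection on the eligibility screen only.** With cut c = Φ⁻¹(q) and Φ₂ the bivariate normal distribution function with correlation r,

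P(not Red at review | Red at entry) = 1 − Φ₂(c, c; r) / q.

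At the central case this is 1 − 0.2376/0.30 = 0.208, and 0.208 × 36 = 7.5 children.

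**Step 2: Red at both eligibility and baseline.** The same model with three screens, by simulation. The central case falls to 12%.

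**Step 3: add SACS-R selection to step 2.** This is closest to the population that the protocol describes, because SACS-R High Likelihood is mandatory and section 6.1 takes every child as Red at baseline.

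| q | r | Step 1 | Step 2 | Step 3, correlation 0.5 | Step 3, correlation 0.7 |
|---|---|---|---|---|---|
| 15% | 0.80 | 39% | 24% | 18% | 15% |
| 15% | 0.90 | 28% | 16% | 12% | 9% |
| 15% | 0.95 | 20% | 11% | 8% | 6% |
| 30% | 0.80 | 30% | 18% | 13% | 10% |
| 30% | 0.90 | 21% | 12% | 8% | 6% |
| 30% | 0.95 | 15% | 8% | 5% | 4% |
| 50% | 0.80 | 20% | 13% | 8% | 5% |
| 50% | 0.90 | 14% | 8% | 5% | 3% |
| 50% | 0.95 | 10% | 6% | 3% | 2% |

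**Step 4: in children.** At the step 3 central case, 0.057 × 36 = 2.1 and 0.079 × 36 = 2.8, so 2 to 3 of 36. Across all step 3 settings the range is 0.019 × 36 = 0.7 to 0.181 × 36 = 6.5 children. Five of the 18 step 3 settings give less than 5%.

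**Step 5: what would be printed.** Exact 95% intervals are 0.7% to 18.7% for 2 of 36 and 1.8% to 22.5% for 3 of 36. Any binomial interval excludes zero once one child crosses, so the interval cannot separate noise from change.

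**The case against.** The strongest reply is that no false inference is planned. Section 6.1 gives counts, percentages and intervals for three categories, with no WellComm test, null value or success threshold. The outcome is secondary, the study is described as exploratory, and section 6.1 says that confounders (maturation is given as an example) cannot be controlled and that any significant effect needs a randomised trial. This stands in part: the reporting is already descriptive, and the defect is confined to one interpretive sentence and the assumed baseline. But the caveat does not withdraw the label. Maturation is real change, whereas the artefact here needs none.

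A second reply is that the artefact may be small. SACS-R selection may leave most children well below the cut. The only related local figure, 50% of a disadvantaged nursery sample with significant language difficulties (section 1.2), comes from a different group but lies at the low-artefact end of the assumed range. This also stands.

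A reader might infer from step 1 that noise would put about 21%, or 7 of 36 children (exact interval 8.2% to 36.0%), in the progressed group. The documents do not support that as a headline. It leaves out the mandatory SACS-R criterion and the requirement, on section 6.1's own account, that children are Red at baseline.

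A reader might also infer that movement out of Red between eligibility and baseline gives a no-effect rate. It does not. Referral screens may be done by outreach workers (section 5.4), while baseline measures are taken by research-team therapists (section 4.2). The interval differs too, and children mature during it.

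**Conclusion.** The concern holds as a fault of definition and labelling. One Amber or Green screen at review shows that a child is no longer Red on that occasion. It does not show clinically significant progress when Red was the entry cut-off, no minimum change is asked for, and the measured baseline is set aside.

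The direction is certain for any reliability below 1; the size is not. With both selection steps applied, the no-change rate is about 2% to 18%, and about 6% to 8% (2 to 3 of 36) at central values. It reaches 10% to 39% only if the eligibility screen alone selects. These figures all rest on assumed reliability, Red prevalence and SACS-R correlation.

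The primary outcome, its test and the sample size are unaffected. The documents do not support a claim that most of any observed movement out of Red would be noise, or that the plan formally attributes it to ECHO.

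**What to change.** In section 6.1:
1. Delete the statement that Amber or Green at review indicates clinically significant progress.
2. Report these children as no longer Red at review, with the binomial interval already planned.
3. Replace the assumption that every child is Red at baseline with a cross-tabulation of the WellComm category measured at baseline against that at review.
4. State that leaving Red may reflect measurement error and selection on a low score as well as maturation, so the percentage is not evidence of an ECHO effect.
5. If eligibility-screen results are available to the study, movement out of Red between eligibility and baseline may be shown as an approximate pre-intervention comparison, marked as differing in assessor and interval.
6. Use no responder label unless a retest-error margin for WellComm can be justified; the protocol gives none.

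The two anchors for the qualifying Red screen (flow chart and section 5.1.1) must be reconciled, since they determine how old that screen can be.

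Cost: a wording change and one extra table. Steps 1 to 4 use screens already scheduled and need no added visits or families. The downside is a less favourable statement of one secondary result.

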7.2 Research Ethics Committee (REC) and Other Regulatory Reviews & Reports

Ethical approval for the ECHO study has been sought from an NHS Research Ethics Committee/Health Research Authority through the Integrated Research Application System (IRAS Number 331323).

Any further changes or amendments to this study protocol will be reviewed and detailed at the beginning of the protocol.

7.2.1 NHS REC Reviewed Research

Before the start of the study, a favourable opinion will be sought from an NHS Research Ethics Committee (REC) for the study and all supporting documents including the protocol, information sheets, informed consent forms and other relevant documents. The study team will be responsible for the maintenance of a study site file or TMF, in which all current and superseded study documents will be retained. Also contained in the site file/TMF will be the approval documentation including correspondence with relevant authorities such as the HRA and REC.

The study team are responsible for producing progress reports throughout the study, including annual reporting (APR) to REC as required. The Chief Investigator will notify the REC of the end of the study and will submit a final report with the results, including any publications/abstracts, to the REC within 12 months of the end of the study. If the study is ended prematurely, the Chief Investigator will notify the REC, including the reasons for the premature termination.

No participants will be enrolled into this research study prior to the study being reviewed by the relevant regulatory authorities and receiving HRA and REC approvals, as well as approval from the R&D Office at Manchester University NHS Foundation Trust.

7.3 Amendments

7.3.1 Studies Involving the NHS

Any amendments to the study shall be reviewed by the Sponsorship Team prior to submission. Any non-substantial amendments shall be notified to the HRA. Any substantial amendments, along with amended documentation, shall be approved by the REC and HRA prior to implementation as per nationally agreed guidelines. The Chief Investigator or designee will work with the R&I department to put the necessary arrangements in place to implement the amendment and to confirm their support for the study as amended.

7.4 Peer Review

The ECHO Intervention Study is being conducted under the request from the Department of Education who determined the need for more evidence of the effectiveness of this intervention. This decision was reviewed and agreed by the Manchester Local Authority and the Head of Service for Speech and Language Therapy at MFT.

An independent peer review was completed by a lecturer in Speech and Language Therapy from the division of Psychology, Communication and Human Neuroscience at the University of Manchester.

7.5 Patient & Public Involvement

The ECHO Intervention was developed by [name] in consultation with families of infants with social communication difficulties. These discussions occurred during regular clinical visits with families, as part of an informal audit of service provision and client needs.

Prior to the development of ECHO, home visits consisted of semi-structured conversations with parents about their concerns and questions regarding their child's communication

Date: 16.05.2024

development, and clinical observations of the adult and child's interactions designed to identify baseline abilities, set targets, and identify intervention outcomes.

Feedback and direct consultation with parents highlighted a number of concerns which needed to be addressed in a programme aimed at parents.

- An understanding that sensory needs and behavioural difficulties are often interlinked but that support for these concerns was required at the same time.
- A general lack of knowledge about the effects of screen-time on child communication and behaviour and how to manage this.
- An awareness that children need to play but difficulties in managing this during a clinical consultation.
- Varied parental understanding of autism and social communication which needs to be addressed through training.

It also highlighted areas of good practice which could support better child engagement with the process, in particular, singing was thought to be helpful and enjoyable for the children.

The ECHO programme responded to parental concerns and preferences in intervention, by offering parents opportunities to discuss their child with clinicians trained and able to impart information and resources about these key points of concern (e.g., sensory needs and screen-time). In addition, ECHO responds to the varied learner needs of the parents regarding social communication, offers play partners for children during parent focused discussions and incorporates singing activities to engage children in the session.

Parents also contributed to the identification of outcome measures suitable for understanding the potential benefits of this programme to both parents and children. In particular, they highlighted potential benefits to parent and child well-being, parental feelings of efficacy, and child communicative ability. Outcome measures were selected with consideration for how well they would capture these changes.

In a second wave of patient involvement, [name] trialled the ECHO Intervention with 12 different families, and participating parents were invited to give further feedback through discussions and an anonymous feedback form. This stage helped refine the intervention further, ensuring it reflected parental concerns. It also generated a consistent model of practice which was recorded in the ECHO Manual. During this process, clinical outcome measures were completed to understand the potential impacts of the intervention, as well as to investigate which outcome measures were suitable to this population.

Clinical experts were included in this process at multiple stages of review. This included discussion and reflection about the observations and parent feedback as interpreted primarily by [name], in order to avoid potential bias. In addition, clinicians trained to deliver the ECHO Intervention were included in consultations and the development of the ECHO Manual.

During the programme development, parents with communication difficulties and neurodivergence were also consulted on their ability to access the programme and understand its content. [name] had conversations with two neurodivergent parents of children with possible neurodivergence to understand their experience of the service. These discussions informed resource development and adaptions within the ECHO Intervention and the study, including the option for Qualitative Study participants to receive

Protocol V.1.1

Date: 16.05.2024

IRAS ID: 331323

interview questions in advance and all ECHO Intervention participants to receive Outcome measure forms in advance, where possible.

Going forward with this project, the parental interviews will offer a systematic means of reviewing the ECHO programme and its future development.

Due to the nature of the funding for this intervention, there is a requirement to evaluate the effectiveness of the intervention.

Research materials were shared with families currently receiving ECHO Intervention for feedback. Parents were given the opportunity to complete questionnaires and feedback about their experience. Their comments were taken into consideration but did not require any change to the research protocol. Parents were also shown the Participant Information Sheets and consent forms and their comments were acted upon.

[name], Principal Investigator, is a steering group member for autism@manchester which is a community funded by the National Institute for Health Research, the Wellcome Trust, and the University of Manchester, to support the collaboration between academics, clinicians, practitioners, autistic individuals and their family and carers, as well as to share knowledge and understanding around autism research.

The research team will engage with autism@manchester at key times across the research life cycle to elicit feedback on materials, protocols, findings, and for dissemination purposes. This will comprise one round of email questions relating to material development and one talk to members of the autism@manchester group at a live event to elicit ideas for interpreting findings and developing the programme for future clinical use.

As funding is not available to pay autism@manchester contributors at this time, the research team will provide a lay summary of findings at the end of the project to autism@manchester as a thank you. Should this project go to a next round of funding the research team will build in costs for consultations with autistic communities at this stage.

